Achieving Equity through Socioculturally-informed, Digitally-Enabled Cancer Pain Management (ASCENT) - Main Trial

IRB# 23-010838

NTC0619810

9.24.2025

IRB Minimal Risk Protocol Template

General Study Information

Principal Investigators: [name], MD, MSCE and [name]

Study Title: Achieving Equity through Socioculturally-informed, Digitally-Enabled Cancer Pain Management (ASCENT) - Main Trial

Protocol version number and date: September 24, 2025 Version 4

Research Question and Aims

Hypothesis

This randomized controlled trial will test a pain-directed intervention whose components have been previously validated in several pragmatic clinical trials: E2C2 (#18-007779), NOHARM (#20-004839) and COPE (#11-008151), delivered remotely to rural dwelling and Hispanic cancer survivors. In a pilot among 42 participants, we refined the sociocultural, linguistic, IT, and clinical aspects of the intervention through iterative design cycles (IRB#23-004139). The ASCENT trial will use a parallel group, two-arm design at eight Mayo Clinic sites with patient-level randomization.

We hypothesize that an EHR-based modular approach that aligns intervention components with a patient's sociocultural, IT, and linguistic needs, will improve pain and physical function to a significantly greater degree than the control condition of enhanced usual care among our target population of Hispanic, rural dwelling, and rural dwelling Hispanic cancer survivors experiencing pain.

Aims, purpose, or objectives

To test a validated collaborative care model-based intervention aimed at improving pain control among rural dwelling and Hispanic cancer survivors by promoting multimodal pain care (MMPC) to reduce inappropriate opioid use and by addressing social determinants of health (SDOH) that impede a patient's access to appropriate care.

Background

Cancer pain is a key case study in health disparities in the US. Cancer pain is prevalent, undertreated, and remains a major cause of suffering, impairment, and disability for millions of Americans. Individual pain interventions and care models show promise for cancer pain in controlled settings. Unfortunately, typical approaches too often target limited aspects of the whole, fail to consider health disparities populations (HDPs), and are unable to serve broad and diverse populations. This situation will only worsen with time. For example, by 2030, the number of already underserved Hispanic cancer survivors in the U.S. will increase to 4 million.

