IVR will be utilized to supplement the collection of PROMs. These PROMs will include the pain assessments used to tailor and individualize the ASCENT intervention, as well as the ASCENT trial outcomes. Trial primary and secondary outcomes will be collected at 3- and 6-months from the patients who do not complete them via Epic Welcome tablet or patient portal. The RevSpring platform will be used to collect IVR data. The IVR data will be maintained on password-protected secure Mayo Clinic servers within the firewall. No PHI data will be released to RevSpring. RevSpring has been used by the Mayo Clinic Spine Center to securely administer follow-up PROMs to over two thousand patients. Data going to the RevSpring platform is transient in nature and is purged once the results are uploaded into Epic. TAP approval has been granted to RevSpring's IVR system and there are Business Associate Agreements (BAA) and Information Security Agreements (ISA) in place, which covers how PHI can be used and stored. The ASCENT pain NRS questionnaire responses will reside on our server and will not go outside of the firewall. Additionally, RevSpring is providing the platform for the texting

capabilities, mentioned in the “follow up touchpoints” section. Study team members will only text study participants and participants will be asked to “opt in” to start receiving the messages.

ASCENT Trial Outcomes

Trial outcomes will include PROMs, healthcare utilization, and employment status. NIH Helping to End Addiction Long-term (HEAL) Initiative Clinical Pain Common Data Elements will be used if validated Spanish translations are available excepting QoL, for which no HEAL measure has been specified. PROMs, **Table 2**, will be administered at baseline by a study coordinator and at 3 and 6 months by a blinded, bilingual, assessor. Valid Spanish translations are available for all PROMs.

Primary outcome The Brief Pain Inventory SF (BPI SF), has been used among diverse populations.⁷⁻⁹ Its psychometric performance characteristics have proven excellent and robust in diverse types and stages of cancer.^{10,11} The BPI SF has been used in disparity-focused trials among Hispanic persons.¹² A Spanish version has been widely used for almost two decades.¹³

Secondary outcomes Will include physical function (PROMIS Physical Functioning SF 6b), quality of life (EQ5D-3L),¹⁴ depression (PHQ-2), anxiety (GAD-2), sleep (PROMIS Sleep Disturbance 6a), and self-reported employment status.

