Mediators Will include self-efficacy for managing symptoms (PROMIS SF 4a), adherence to behavioral MMPC plan components (logged count data), use of ASCENT e-tools (minutes/week), social isolation (PROMIS SF 4a), informational support (PROMIS SF 4a), and opioid consumption in oral morphine equivalents (OMEs) collected via EHR prescriptions.

Health care utilization Healthcare utilization for ASCENT will consider hospitalizations and ED visits which will be ascertained using EHR entries and administrative billing data. Data collected for hospitalizations will include admission and discharge diagnoses, length of stay, whether an admission was planned for anti-cancer treatment or unplanned. The majority, but not all, of patients’ health care utilization will occur at MC facilities. Established patterns suggest that 80% of patients care will occur at an MC facility. However, we will use imputation methods and sensitivity analyses to assess the impact of mis-ascertainment of utilization data.

Measure	Domain	Items	Time min.	HEAL data	Collected 0,3,6 mo.
Primary					
BPI SF	Pain	7	3	✓	✓
Secondary					
PROMIS SF	Physical Function	4	2	✓	✓
EQ-5D-3L	QoL	5	2.5		✓
PHQ-2	Depression	2	2	✓	✓
GAD-2	Anxiety	2	1	✓	✓
PROMIS SF	Sleep	6	3	✓	✓
Mediators					
PROMIS SF	Self-efficacy	4	2		✓
PROMIS SF	Social isolation	4	2		✓
PROMIS SF	Informational support	4	2		✓

Risks and Benefits

The risks of the ASCENT trial study are minimal as participants are being potentially offered additional support and expertise to manage pain. Nothing in this trial will impede patients them from receiving whatever pain

treatment they and their team agree are appropriate and evidence-based. The benefits to patients include the potential for safer and more guideline-concordant pain management and lower risk of opioid exposure and dependency.

Protection of Human Subjects

Care will be taken to ensure that patients' data are protected. Data from chart review, patient-reported preferences, and patient-reported outcomes will be stored securely on password protected Mayo Clinic research servers within the firewall. Clinicians will still be able to make professional judgments about the appropriateness of engaging patients in specific conversations about pain management throughout their post-surgical recovery and may disregard EHR-prompts as appropriate.

Subject Information

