- The study plans to conduct a retrospective chart review and ask subjects to complete a questionnaire.
- The study plans to include subjects previously diagnosed with a specific disease and add newly diagnosed subjects in the future.

The study will use data that have been collected under another IRB protocol. Include in the Methods section and enter the IRB number from which the research material will be obtained. *When appropriate, note when subjects have provided consent for future use of their data and/or specimens as described in this protocol.*

Enter one IRB number per line, add more lines as needed

Data Specimens Data & Specimens _____

Data Specimens Data & Specimens _____

Data Specimens Data & Specimens _____

Data Analysis

All methods will be appropriate for a patient-randomized, multi-site study. In addition, because our primary aim is to assess effectiveness in two potentially overlapping subgroups, we will use a Sidak corrected alpha of $\alpha = 0.0253^{15}$ to assess significance. We will summarize patient characteristics by study arm, and report standardized mean differences (SMDs) to assess balance; we will do this for the entire cohort as well as separately for Hispanic and rural patients. Then, to assess the effectiveness of the intervention on the primary and secondary outcomes we will estimate a series of generalized linear models, each estimated separately for Hispanic and rural patients, respectively, with outcome as dependent variable and intervention status indicator. Each model will be specified with a link and distribution appropriate for the outcome, e.g., logit or linear, and include indicators for randomization factors and any characteristics that have $SMD > 0.1$ across groups. By testing whether the coefficient of the intervention status differs from zero we can assess whether the intervention has an impact on the outcome.

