Exploratory Subaims: We will undertake several exploratory analyses. First, to gain insights into the intervention pathways we will undertake a mediation analysis including only patients randomized to the intervention group. This will employ structural equation models, which will allow us to partition the overall effect of the intervention into direct and indirect effects and compare their magnitude.^{16,17} The results of these analyses will provide information about the relative importance of the mediators on the intervention effect. A second exploratory aim will assess whether there are particular subgroups of patients in which the overall intervention is more effective. Rather than prospectively identify subgroups as in a conventional heterogeneity of treatment effect analysis, we propose to use machine learning tools to cluster intervention patients that respond well or poorly to the intervention. Specifically, we will use a 2/3 random sample of intervention patients to train an unsupervised hierarchical clustering algorithm to identify clusters of patients based on all baseline factors; hierarchical clustering is a machine learning approach that requires no assumptions about numbers of clusters or the relationships between factors, and has been used previously to cluster patients into similar groups.^{18,19} Clusters will then be assessed for relative treatment effectiveness by including cluster indicators in the main models, along with interactions with the intervention indicator. This will allow us to identify clusters which have higher or lower response to the intervention. Finally, we will validate these results using the 1/3 remaining (validation) sample. The results of this aim will provide insights into the types of patients for which the intervention is likely to be most or least effective.

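### Prescribed opioid use is placed only among the mediators and analysed only within the intervention arm, so no planned analysis can show whether ASCENT changes it

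*Protocol*

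**What the plan says.** Under Aims, purpose, or objectives, the protocol describes an intervention meant to improve pain control, and gives two routes. One is social determinants of health. The other works "by promoting multimodal pain care (MMPC) to reduce inappropriate opioid use". Risks and Benefits adds "lower risk of opioid exposure and dependency" to the potential benefits for patients.

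Under ASCENT Trial Outcomes, the opioid variable appears in the Mediators paragraph, as "opioid consumption in oral morphine equivalents (OMEs) collected via EHR prescriptions". It is called consumption, but the source is prescriptions.

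Two parts of Data Analysis decide what happens to it. The main models are described this way: "to assess the effectiveness of the intervention on the primary and secondary outcomes we will estimate a series of generalized linear models". They are fitted separately for Hispanic and rural patients and test the coefficient of intervention status. For mediators, the Exploratory Subaims say "we will undertake a mediation analysis including only patients randomized to the intervention group", using structural equation models that are to split the intervention's overall effect into direct and indirect components.

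**The concern.** The protocol names opioid reduction as part of how the intervention works and as something patients may gain, but plans no contrast with the control arm that would show whether it happens.

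A change in OME seen only among intervention patients could not be attributed to ASCENT. Participants are selected for a pain score of at least 5 out of 10, so pain, and the prescribing that follows it, may fall over six months through regression to the mean or recovery. General prescribing trends would act in the same direction or against it. The control arm is what removes these explanations.

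The reading of the primary result is also affected. Less pain together with lower, equal or higher opioid prescribing would mean three different things for an intervention described in these terms.

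**Working it through.** **1. Where OME stands among the variables (ASCENT Trial Outcomes).**

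- General statement: "Trial outcomes will include PROMs, healthcare utilization, and employment status". OME is not a PROM and is not named.
- Primary: BPI SF.
- Secondary: physical function, quality of life, depression, anxiety, and then "sleep (PROMIS Sleep Disturbance 6a), and self-reported employment status". No opioid measure.
- Utilization: "Healthcare utilization for ASCENT will consider hospitalizations and ED visits". No prescribing measure.
- Mediators: OME is listed here, and only here.

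**2. Which analysis takes which variables (Data Analysis).** The between-arm models are stated for the primary and secondary outcomes. The mediator analysis is stated for intervention patients only. OME is in the second set and not in the first, so the number of between-arm estimates of opioid use in the plan is 0.

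**3. What an intervention-only mediation analysis can estimate.** Let Z be the randomised arm, M the mediator (OME) and Y the outcome (pain). In the simple linear case:

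- M = i₁ + aZ + e₁
- Y = i₂ + c′Z + bM + e₂
- total effect c = c′ + ab, where ab is the indirect part and c′ the direct part
- a = Cov(Z, M) / Var(Z)

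If only intervention patients are included, Z = 1 for everyone, so Var(Z) = 0, Cov(Z, M) = 0, and a = 0/0 is undefined. The same holds for c and c′. Only b remains, the association of OME with pain among treated patients. That does not say whether ASCENT changed OME, and it gives nothing to partition. A more elaborate structural equation model does not help, because the missing ingredient is variation in assignment.

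**4. The protocol's own sample size, and what it would imply for OME.** Inputs from the Sample size section: standardized effect 0.40, alpha 0.0253, power 90%, 10% loss, overlap factor 1.9.

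- n per arm = 2(z₁₋α/₂ + z₁₋β)² / d² gives 155 by normal approximation; the t-test solution is 155.99, so 156, as stated.
- 312 × 1.9 / 0.9 = 658.7, so 659, as stated. 659 × 0.9 = 593.1, so 593, as stated.

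The detectable effect at 90% power and two-sided alpha 0.05 is (1.960 + 1.282) × √(2/n per arm):

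| Comparison | n per arm | Detectable effect |
|---|---|---|
| Within one group of 312 | 156 | 3.242 × √(2/156) = 0.37 SD |
| All 593 pooled | 296.5 | 3.242 × √(2/296.5) = 0.27 SD |

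These figures are illustrative only. They assume a roughly normal or suitably transformed measure, and the protocol gives neither an SD for OME nor the proportion of patients with none prescribed.

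**5. Capture.** The Health care utilization paragraph expects about 80% of care at the sponsor's facilities. Assume that prescriptions follow the same pattern and that the loss is equal in both arms. An absolute mean difference in OME would then be observed at about 0.8 of its true size, while a ratio of means would be unchanged. If the intervention moves care into or out of the system, neither holds.

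**The case against.** A reader might infer that a stated aim of the trial goes unanswered. The documents do not support that. The object of the aim sentence is pain control, and opioid reduction is worded as one route to it. The hypothesis names only pain and physical function, and both are compared between arms. Listing opioid use as a mediator fits its role as a route, and the wording in Risks and Benefits describes potential benefit and does not set an endpoint. What stands against this is narrower: a claimed route still needs evidence that the intervention moves it, and that evidence needs the control arm.

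A reader might also infer that the data for the comparison are already extracted. The protocol says only that OME comes from EHR prescriptions. It does not limit this to one arm, but it does not say that controls are abstracted either.

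The list of models may not be exhaustive. Healthcare utilization, for example, is a trial outcome but is missing from the secondary list, and an SAP could add an OME comparison. The protocol itself, however, assigns OME to the mediators and restricts mediation to one arm. That restriction is a stated choice, and it defeats the stated purpose of the analysis. It may have been made because some listed mediators, such as adherence to plan components, have little meaning for controls. Prescribed OME does not share that difficulty.

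Two further points stand. Total OME does not measure inappropriate use: the Background describes both under- and over-prescribing, so better care could raise OME in some patients and lower it in others. And the exploratory results are declared hypothesis-generating and descriptive, which limits the harm.

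**Conclusion.** The point holds in this form: the protocol gives opioid use a role in how ASCENT works, plans no between-arm comparison of it, and confines its only analysis to a sample in which the arm's effect on it cannot be estimated. The same analysis cannot deliver the direct and indirect effects that the Exploratory Subaims promise. This follows from reading the sections together and from Var(Z) = 0. It rests on no assumed figure.

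The consequence is limited. The primary and secondary comparisons are untouched. What is lost is a valid estimate of the effect on prescribed opioids and of the pathway through them. The detectable effects of 0.37 and 0.27 SD show only the order of effect that the planned sample might detect on a well-behaved scale. They do not establish adequate power for OME.

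**What to change.** 1. Name EHR-prescribed OME as a secondary or supportive outcome and compare it between randomised arms. Use the same covariate adjustment as the main models, in a form suited to zeros and skew (a two-part or log-link model, for instance), and report estimates with confidence intervals.
2. Run the OME mediation analysis in both arms with the randomised arm as the exposure. Keep it exploratory: OME itself is not randomised, and pain drives prescribing, so the mediator-outcome path remains open to confounding even then.
3. State that OME is prescribed and not consumed, and that capture is limited to the sponsor's system, with about 80% of care expected there.
4. Either define inappropriate use so that it can be measured, or limit the conclusion to prescribed opioid exposure. A difference in mean OME alone would not show that inappropriate use fell.

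The cost is one line in the outcome list, one more model and one more secondary estimate to interpret. OME must also be abstracted from the EHR for control patients if this is not already planned. No new data source or patient contact is needed.

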C.9.viii. Sample size. Our sample size is determined by the number of patients needed to detect a standardized effect of 0.40 between intervention groups, within either the Hispanic or rural subgroup of patients. The choice of 0.40 SD was informed by the 11-point NRS pain score, which we expect to closely align with the BPI. In preliminary analyses using data from the ongoing E2C2 study,²⁰⁻²² we found the standard deviation for the NRS pain score to be 2.7 for Hispanic cancer patients and 2.5 for rural dwelling cancer patients. Thus 0.40 SD corresponds to approximately a 1 point difference in the NRS pain score; 0.40 also conventionally corresponds to a 'medium' effect size.²³ Notably, a 1-point difference on the BPI as well as other 0 to 11 pain NRS has been shown to be a clinically important difference.^{24,25} The sample size needed to detect a standardized effect of 0.40

with a power of $1-b = 90\%$ and an $a = 0.0253$ (Sidak adjusted for 2 comparisons) is 156 per arm or 312 per group. We anticipate that approximately 10% participants will be rural dwelling Hispanics, based on the fact that ~90% of Hispanic cancer survivors treated at the Mayo Clinic Comprehensive Cancer Center are urban dwelling, RUCA 1 and 2, so assume approximately 10% overlap between the two groups. Allowing for a 10% loss to followup, we therefore plan to enroll $312 \times 1.9/(90\% \text{ followup}) = 659$ patients, of whom at least 50% are Hispanic and 50% rural dwelling.. For other outcomes, we assume followup on 593 patients and will have 90% power to detect a smaller standardized effect of 0.3 with an uncorrected $a = 0.05$. The exploratory subaim will be used to generate hypotheses for further work; results will be descriptive, with confidence intervals reported as appropriate.

References

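### The fixed Sidak level of 0.0253 for both group-specific primary tests is valid but less efficient than its step-down version, which keeps the same 5% family-wise error

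*Protocol*

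**What the plan says.** The Data Analysis section of the protocol gives the reason for the correction: "our primary aim is to assess effectiveness in two potentially overlapping subgroups, we will use a Sidak corrected alpha", set at 0.0253. The outcome models are "each estimated separately for Hispanic and rural patients, respectively, with outcome as dependent variable and intervention status indicator", and the decision is made "By testing whether the coefficient of the intervention status differs from zero". That makes two primary tests, one per group, each judged against the same fixed level.

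The sample size section (C.9.viii) uses the same level. The aim is to "detect a standardized effect of 0.40 between intervention groups, within either the Hispanic or rural subgroup of patients" with 90% power, and the result is given as "Sidak adjusted for 2 comparisons) is 156 per arm or 312 per group". About 10% overlap between the groups and 10% loss to follow-up bring enrolment to 659.

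The protocol contains no step-down or step-up rule, and nothing lets the level for one group change once the other has been declared significant.

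**The concern.** With two hypotheses, once one null has been rejected at 0.0253 at most one true null can remain. Protecting the family-wise error then no longer requires the second test to be held at 0.0253; 0.05 is enough. Under the stated rule, a group with p between 0.0253 and 0.05 is reported as negative even when the other group is clearly positive.

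Two things are at stake: some power on a sample size already fixed, and the chance of a report that the intervention works in one underserved population but not the other when the true effect is the same in both.

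**Working it through.** **Inputs.** From the protocol: level 0.0253 for two comparisons, 0.40 SD within each group, 90% power, 156 per arm and 312 per group, about 10% overlap, 10% loss to follow-up. Inferred: two-sided tests and 1:1 allocation. Neither is stated outright, but the two-sided calculation reproduces the stated sample size and the one-sided one (131 per arm) does not. The NRS standard deviations of 2.7 and 2.5 cancel in the standardised effect.

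**The plan's own figures.**
- Sidak level: 1 − (1 − 0.05)^(1/2) = 0.02532. Agrees.
- Sample size per arm, two-sample t-test, 0.40 SD, two-sided 0.0253, 90% power: 155.99, so 156. Agrees (the normal approximation gives 155).
- Enrolment: 312 × 1.9 / 0.90 = 658.7, so 659. Agrees.

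**Correlation between the two tests.** Two groups of 312 in a union of 312 × 1.9 = 592.8 share 624 − 592.8 = 31.2 patients. As a share of 312 this is 0.10, taken as the correlation between the test statistics.

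**Why step-down holds the error rate.** It is the closed test: the joint null is tested by Sidak and each single null at 0.05. If both nulls are true, an error needs at least one p-value at or below 0.0253, exactly as under the stated rule. If one null is true, it can be rejected only when its own p-value is at or below 0.05. The overlap adds no assumption beyond those single-step Sidak already makes.

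**Hand check at correlation 0.** The non-centrality is 0.40 × √(156/2) = 3.533. Under the normal approximation, single-test power is 0.9025 at 0.0253 and 0.9421 at 0.05.
- Stated rule, both groups: 0.9025² = 0.8145.
- Step-down, per group: 0.9025 + (0.9421 − 0.9025) × 0.9025 = 0.938.
- Step-down, both groups: 0.9421² − (0.9421 − 0.9025)² = 0.886.
- One null true, error in that group under step-down: 0.0253 + (0.05 − 0.0253) × 0.9025 = 0.0476, against 0.0253 under the stated rule.

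**Results at correlation 0.10** (bivariate normal probabilities, confirmed by simulation of 2 million pairs):

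| Quantity | Stated rule | Holm-Sidak |
|---|---|---|
| Power per group, 0.40 SD in both | 90.3% | 93.7% |
| Power for both groups | 81.8% | 88.7% |
| Exactly one group significant | 16.9% | 10.0% |
| At least one group significant | 98.7% | 98.7% |
| Family-wise error, both nulls true | 5.0% | 5.0% |
| Only one group benefits: power in that group | 90.3% | 90.4% |
| Only one group benefits: false positive in the other | 2.5% | about 4.7% |

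**Sensitivity to effect size.** At 0.30 SD in both groups, with the same sample and correlation, power per group goes from 66.0% to 72.1% and for both from 44.9% to 57.1%.

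**The case against.** The stated rule is a recognised, pre-specified method, and it agrees with the sample size, which reproduces and meets its 90% target. All of that stands. A reader might infer that the primary analysis is invalid or underpowered; the protocol's figures do not support that.

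A reader might also infer that single-step Sidak gives no error protection in return for the lost power. That goes too far. The rules tie on the family-wise error when both nulls are true, but when only one group benefits the stated rule has the lower false-positive rate in the other (2.5% against about 4.7%). Step-down remains within 5%, the limit the correction is there to hold, but the difference is real. The stated rule also yields simultaneous intervals that agree with its test decisions, and step-down gives up part of that.

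A third tempting reading is that the trial succeeds only if both groups show benefit. The hypothesis names Hispanic, rural and rural Hispanic survivors as the target population but sets no both-must-win rule, and the sample size section speaks of detecting an effect within either group. If both were required, each could be tested at 0.05 without correction, giving 88.9% for both. The 7-point gain for both groups therefore describes a result the investigators would presumably welcome, not the protocol's definition of success.

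Finally, the figures come from an unadjusted two-sample comparison, while the protocol plans adjusted models. If adjustment removed 25% of the outcome variance (an assumption, not a protocol figure), the non-centrality would be 3.533/√0.75 = 4.08. Power per group would then go from 96.7% to 98.2%, and for both groups from about 94% to about 97%. The gain shrinks but keeps its direction.

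**Conclusion.** The point holds as a question of efficiency. The protocol fixes a valid rule that is uniformly less powerful than its step-down version at the same 5% family-wise error. The gain is about 3.5 points per group and 7 points for both groups, with split results falling from about one in six to one in ten. It depends on a true effect of 0.40 SD in both groups, 156 evaluable patients per arm in each group, a correlation near 0.10, two-sided tests and 1:1 allocation. The correlation matters little: at zero, power for both groups goes from 81.5% to 88.6%. There is no gain in the chance of showing benefit in at least one group, and essentially none if only one group benefits.

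This is a cheap improvement to a rule the protocol itself states, not a missing detail and not a correction of an error.

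**What to change.** For the primary outcome, replace the fixed level with this rule in the protocol, and in the SAP to match: test the smaller of the two group-specific p-values at 0.0253; if it is significant, test the other at 0.05; if it is not, declare neither. Leave the sample size unchanged, and report single-step 97.47% intervals for both groups as the simultaneous intervals.

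The change needs no extra patients or data, but it alters the primary decision rule. It must be made and dated before outcome data are seen; the protocol does not give enrolment status, so the sponsor should confirm that this is still possible. The text should state both downsides: the rise from 2.5% to about 4.7% in the false-positive rate for a non-benefiting group when the other benefits, and the possibility that a 97.47% interval includes zero for a group declared at the second step.

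### The protocol plans no estimate of the BPI effect in all randomised patients and no comparison of the Hispanic and rural effects; one supportive model would supply both

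*Protocol*

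**What the plan says.** The Hypothesis section of the protocol expects better pain and function than enhanced usual care "among our target population of Hispanic, rural dwelling, and rural dwelling Hispanic cancer survivors experiencing pain".

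The Data Analysis section adopts a Sidak-corrected alpha of 0.0253 "because our primary aim is to assess effectiveness in two potentially overlapping subgroups". Models for the primary and secondary outcomes are "each estimated separately for Hispanic and rural patients, respectively, with outcome as dependent variable and intervention status indicator". The decision rule is: "By testing whether the coefficient of the intervention status differs from zero we can assess whether the intervention has an impact on the outcome". The cohort as a whole is mentioned in that section only for summarising baseline characteristics and balance.

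The exploratory subaims look for variation in response through data-driven clusters, "Rather than prospectively identify subgroups as in a conventional heterogeneity of treatment effect analysis". The mediation analysis is restricted to the intervention arm.

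The sample size section (C.9.viii) plans 156 per arm and 312 per group for 0.40 SD with 90% power at 0.0253. It assumes about 10% overlap and enrols 659. For other outcomes it assumes 593 followed patients and claims 90% power for 0.3 SD at an uncorrected 0.05.

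**The concern.** Three things do not fit together.

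- The hypothesis covers a target population made up of both groups and their overlap, but no effectiveness model is fitted to that population.
- Each group gets its own test against zero, but no estimate says whether the two effects differ. One significant and one non-significant test is not evidence of a difference.
- The power statement for the other outcomes needs all 593 patients in one analysis, while the analysis text models those outcomes group by group.

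At stake is how a split result would be read. In a trial about equity, a non-significant test in one group is easily taken to mean that the intervention fails there, and the plan offers no number to check that reading. The most precise effect estimate the trial can produce is also left unplanned.

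**Working it through.** **Inputs** (protocol, Data Analysis and C.9.viii): alpha 0.0253 per group; 156 per arm, 312 per group; effect 0.40 SD; power 90%; overlap about 10%; loss to follow-up 10%; 593 followed. Assumptions: two-sided tests (sidedness is not stated, but two-sided reproduces the n), 1:1 allocation (implied by 156 of 312), one time point and no gain from covariates.

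**Reproducing the plan's figures.** Sidak alpha = 1 − 0.95^(1/2) = 0.0253. With 156 per arm the noncentral t test has power 0.900. Enrolment = 312 × 1.9 / 0.9 = 658.7, so 659. Followed = 312 × 1.9 = 592.8, so 593. All agree with the protocol.

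**Chance of a split result under equal true effects.** Power per group = Φ(δ√(n/2) − z). With z = 2.237 for alpha 0.0253: 0.40 × √78 − 2.237 = 1.296, giving 0.9025. P(exactly one significant) = 2 × (power − P(both)). P(both) comes from a bivariate normal whose correlation is the shared fraction of patients. The overlap is 2 × 312 − 593 = 31 patients, and 31/312 = 0.099.

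| Common true effect | Assumption on overlap | P(exactly one significant) |
|---|---|---|
| 0.40 SD | independent, exactly 90% power: 2 × 0.9 × 0.1 | 18.0% |
| 0.40 SD | independent, power 0.9025 | 17.6% |
| 0.40 SD | correlation 0.10 | 17.0% |
| 0.40 SD | 10% of all participants shared (326 per group, correlation 0.18) | 14.5% |
| 0.40 SD | no overlap, 296 per group | 20.2% |
| 0.35 SD | correlation 0.10 | 30% |
| 0.30 SD | correlation 0.10 | 42% |
| 0.25 SD | correlation 0.10 | 47% |
| 0.45 SD | correlation 0.10 | 8% |

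**What a split can look like.** A group estimate is significant above 2.237 × 0.1132 = 0.253 SD. Estimates of 0.27 and 0.23 SD would split, although they differ by only 0.04 SD.

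**Precision of the missing estimates.**

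- Per group: SE = √(4/312) = 0.113 SD.
- All followed patients: SE = √(4/593) = 0.082 SD. The ratio is 0.725, so the SE is 27% smaller.
- Difference between the two overlapping group effects: SE = 0.1132 × √(2 × (1 − 0.099)) = 0.152, 95% half-width 0.30 SD.
- Hispanic-only against rural-only (312 − 31 = 281 each): SE = √(8/281) = 0.169, half-width 0.33 SD, and about 66% power for a 0.40 SD difference in effect.

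**Power claim for the other outcomes** (0.30 SD, alpha 0.05).

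- 593 patients: 0.30 × √(296.5/2) − 1.960 = 1.693, power 95.5%. The effect detectable with 90% power is 0.27 SD, consistent with the stated 0.3 after rounding.
- 312 patients: 0.30 × √78 − 1.960 = 0.690, power about 75%.

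The claim therefore holds for a whole-cohort analysis and not for the group-wise models described.

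**The case against.** The strongest case against is that the design is coherent. The stated primary aim is effectiveness in two subgroups, and the alpha, sample size and models all follow from it. Type I error is controlled. Supportive pooled and between-group estimates are often left to a statistical analysis plan, which is not shown here, and nothing in the protocol forbids them. The 17-18% is simply what 90% power implies for two nearly independent tests, and adding a model does not change it. The hypothesis lists the component groups and can be read group by group, and since equal numbers are recruited on purpose, a pooled effect averages over a mix set by design. The exploratory sentence about heterogeneity introduces a search for responder clusters and does not address Hispanic versus rural.

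Most of this stands. A reader might infer that the separate tests are an error, or that the protocol will declare the intervention effective in one group and not in the other. The documents support neither: the tests match the aim, and the protocol nowhere draws that conclusion. Nor is there reason to replace the primary estimator with a model of three membership cells, since the cell belonging to both groups would hold only about 31 patients.

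What does not fall away is internal to the protocol. It already fixes the models as group-wise, and its own power statement for the other outcomes relies on a whole-cohort analysis that this text does not contain.

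**Conclusion.** The point holds as a recommended improvement, not as a fault in the primary tests. The plan lacks an effect estimate in all randomised patients and any estimate of the difference between the group effects, and its analysis and sample size sections disagree on the population for the other outcomes.

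The 17-18% is conditional on a common true effect equal to the planned 0.40 SD. It is not a worst case, because smaller common effects of 0.25 to 0.35 SD give 30-47%. It measures how often the question of interpretation will arise, not an error rate that the fix reduces. The gain is an overall estimate with a 27% smaller SE and the only direct estimate of whether benefit differs. That second estimate is too imprecise to serve as a powered test.

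**What to change.** Keep the two group models as the primary tests at 0.0253. Add to the Data Analysis section:

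1. One supportive model in all randomised patients, each counted once and adjusted for the randomisation factors, reporting the overall BPI effect with a 95% CI.
2. From a treatment-by-group term, the Hispanic-versus-rural difference in effect with a 95% CI, presented as an estimate. State how patients who are both rural and Hispanic enter this term.
3. A sentence that any difference in benefit between groups will be judged from that interval, and not from one significant and one non-significant group test.
4. The same whole-cohort model for the other outcomes, so that the analysis text agrees with the 593 patients in the sample size section.

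The cost is a few lines of text and one more model, with no added patients, data or alpha. The downside is small: a between-group interval wide enough that it will often be inconclusive.
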